
A. Inclusion Criteria

1. Patient is at least 18 years of age.
2. Patient qualifies for a primary cementless tibia total knee arthroplasty based on physical exam and medical history, including diagnosis of severe knee pain and disability due to at least one of the following:
 - a. Rheumatoid arthritis, osteoarthritis, traumatic arthritis, polyarthritis.
 - b. Collagen disorders and/or avascular necrosis of the femoral condyle.
 - c. Post-traumatic loss of joint configuration, particularly when there is patellofemoral erosion, dysfunction or prior patellectomy.

- d. Moderate valgus, varus, or flexion deformities.
- e. The salvage of previously failed surgical attempts that did not include partial or total knee arthroplasty of the ipsilateral knee.
- 3. Patient has participated in the study-related Informed Consent process.
- 4. Patient is willing and able to provide written Informed Consent by signing and dating the IRB approved Informed Consent Form.
- 5. Patient is willing and able to complete scheduled study procedures and follow-up evaluations as described in the Informed Consent Form.
- 6. Independent of study participation, patient is a candidate for commercially available cementless *NexGen* TM tibial knee component, implanted in accordance with product labeling.

B. Exclusion Criteria

- 1. Previous history of infection in the affected joint.
- 2. Active local or systemic infection that may affect the prosthetic joint.
- 3. Insufficient bone stock on femoral or tibial surfaces.
- 4. Skeletal immaturity.
- 5. Neuropathic arthropathy.
- 6. Osteoporosis or any loss of musculature or neuromuscular disease that compromises the affected limb.
- 7. A stable, painless arthrodesis in a satisfactory functional position.
- 8. Severe instability secondary to the absence of collateral ligament integrity.
- 9. Rheumatoid arthritis accompanied by an ulcer of the skin or a history of recurrent breakdown of the skin.
- 10. Patient has previously received partial or total knee arthroplasty for the ipsilateral knee.
- 11. Patient is currently participating in any other surgical intervention studies or pain management studies.
- 12. Patient is known to be pregnant or considered a member of a protected population (e.g., prisoner, mentally incompetent, etc.).
- 13. Patient has a known or suspected sensitivity or allergy to one or more of the implant materials.

VIII. Study Device Information

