After completing the Informed Consent process, candidates who agree to enter the study must sign and date the IRB approved Informed Consent Form. The Informed Consent Form must be signed and dated prior to study data collection and the date of study surgery. For bilateral TKA candidates that agree to enroll for both operative sides, a separate Informed Consent Form must be signed and dated for each operative side.

A copy of the signed Informed Consent Form should be provided to the subject. The original signed Informed Consent Form is to be filed in the subject's study binder.

Study data will not be collected until the Informed Consent Form has been signed and dated. If the candidate does not wish to participate (does not sign and date the Informed Consent Form), data for that candidate will not be collected for this study.

C. Subject Enrollment

Once the Informed Consent Form has been signed and dated by the subject, the subject will be considered enrolled in the study. A unique case identification number (Case ID) will be assigned to each participating subject/knee (bilateral subjects will be assigned a unique case ID number for each knee). This unique case ID number will be used throughout the study for identification.

Case ID numbers will be assigned consecutively in ascending order per site, with the starting number for a given site defined by the Sponsor.

The subject will be considered an active study subject after receiving the study device during surgery. In the event that a subject does not receive the study device at the time of surgery, a **Study Completion** form must be submitted and this will be documented as a screen failure.

D. Subject Enrollment Log

A **Subject Enrollment Log** (Appendix C) will be maintained at the site throughout the course of

the study and filed in the site Regulatory Binder. The purpose of the log is to provide documentation that all enrolled study subjects underwent the Informed Consent process. All candidates who sign and date the approved Informed Consent Form for the study must be entered in the log. If a subject signs and dates additional Informed Consent Form(s) after enrollment (e.g., due to a protocol amendment, protocol revisions, etc.), subsequent signings will also be recorded in the log. The proposed date of surgery for each subject will also be added to the log.

E. Monitor Log

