The **Monitoring Visit Log** (Appendix C) will be maintained throughout the course of the study. The log will contain the visit date, monitor name/signature and the purpose of the visit (i.e. site initiation, onsite interim monitoring, site close-out, etc.). The monitoring visit log will be filed in the site Regulatory Binder for the study.

F. Delegation of Authority

A **Delegation of Authority Log** (Appendix C) will be maintained throughout the study and will contain the names, initials, signatures and study responsibilities of all site personnel/designees involved in study procedures and data collection. The **Delegation of Authority Log** will be filed in the site Regulatory Binder for the study.

G. Preoperative Data Collection

Preoperative data will be collected on the following source documents:

1. Inclusion/Exclusion Criteria
2. Demographic Evaluation
3. Physical Exam
4. Forgotten Joint Score (FJS-12)
5. Oxford Knee Score
6. UCLA Activity & Satisfaction Survey
7. Protocol Deviation (as applicable)
8. Study Completion (as applicable)

H. Surgical Technique

Standard operative procedures will be followed and all surgical procedures will be performed under aseptic conditions. Investigators will implant all commercially available *NexGen TM Tibia* implants and any other compatible products in compliance with corresponding labeling requirements and in accordance with appropriate surgical technique(s), found on www.zimmerbiomet.com. NexGen TM Tibia implants in this study must be implanted cementless, without the use of autograft bone paste slurry.

I. Surgical and Immediate Post-Surgical Data Collection

Surgical and immediate post-surgical data will be collected on the following source documents:

1. Surgical & Discharge Information
2. Physician Assessment of Postop Radiographs
3. Adverse Event Report (as applicable)
4. Protocol Deviation (as applicable)
5. Study Completion (as applicable)

Post-surgical management for study subjects will follow the investigator's standard of care for patients undergoing total knee arthroplasty (e.g. prophylactic antibiotic therapy, prevention of deep vein thrombosis, prevention of pulmonary embolism, etc.). Post-surgical rehabilitative therapy will be as prescribed by the investigator.

J. Postoperative Follow-up Data Collection

Postoperative follow-up clinical evaluations will be conducted at the following visit intervals:

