Clinical Interval	Interval Window in Days Postop*	Approximate Window in Weeks or Months Postop
6 weeks	28 to 56 days	± 2 weeks
6 months	151 to 214 days	± 1 month
1 year	333 to 396 days	± 1 month
2 years	669 to 791 days	± 2 months

*Visit(s) outside of window will be determined based on Days Postop

Postoperative follow-up clinical data will be collected on the following source document forms:

1. Physical Exam
2. Physician Assessment of Postop Radiographs
3. Forgotten Joint Score
4. Oxford Knee Score
5. UCLA Activity & Satisfaction Survey
6. Adverse Event Report (as applicable)
7. Protocol Deviation (as applicable)
8. Study Completion (as applicable)
9. Implanted Device Form (as applicable)

Subjects will be followed postoperatively for 2 years. Unless the study is otherwise closed, data will continue to be collected until the subject completes the study per the protocol, voluntarily withdraws from the study, is withdrawn from the study by the investigator, is lost to follow-up, undergoes revision to remove a study device, or expires. See Management of Incurrent Events (Section X, Subsection D of this protocol) for additional details. Reason(s) for study completion must be documented on the **Study Completion** form.

K. Minimization of Subjects Lost to Follow-up

Subject follow-up is extremely important for the conduct of a clinical study, and the expectation is to maintain the highest possible rate of follow-up compliance throughout this study. During the informed consent process and at each follow-up interval, subjects should be counseled on the importance of completing future study follow-up intervals.

L. Radiographic Definitions and Methods

All postoperative radiographs will be evaluated by the Investigator and documented using the **Physician Assessment of Postop Radiographs**. An **Adverse Event Report** must be completed for findings identified as an adverse event.

It is the Investigator's responsibility to review radiographs for image quality during the subject's clinical visit and prior to uploading into the image collection service. Radiographic images must show an orthogonal view of the tibial implant interface. If the Sponsor determines a radiograph is of poor quality, then the site must reschedule the subject for additional radiographs.

1. Required radiographic views

Radiographic Interval	Interval Window	Required Radiograph
Immediate Postop	Pre weight-bearing	AP and Lateral
6 weeks	± 2 weeks	AP and Lateral

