The Investigator can choose to withdraw a subject from the study if the subject no longer meets study inclusion/exclusion criteria. The reason for the Investigator's withdrawal of the subject must be documented on the **Study Completion** form.

5. **Subject Withdrawal**

Study subjects may choose to withdraw from the study at any time, for any reason. If possible, a final evaluation will be completed for any subject who no longer wishes to participate in the study. The reason for the subject withdrawal must be documented on the **Study Completion** form.

6. **Lost to Follow-up**

A study subject will be considered lost to follow-up after they have missed a visit and attempts to locate and evaluate the subject using the procedure outlined below have failed. All attempts to contact the subject are to be documented in the subject's medical record and on the **Study Completion** form. Missed visit(s) also must be documented using the **Protocol Deviation** form, unless the visit is retrospective. The first three contact attempts should be made by telephone, with additional attempts as outlined in the following table:

If	Then
a response is not received after three (3) phone calls	the Investigator or Designee should send a letter to the subject explaining the follow-up agreement per the Informed Consent, and requesting a response from the subject.
all attempts to contact the subject are unsuccessful or the subject is contacted and chooses to withdraw from the study	a Study Completion form will be completed and will specify the reason the subject is no longer participating in this study.

7. **Protocol Deviations**

Investigators should not deviate from the study protocol. If a protocol deviation does occur, the deviation must be documented on the **Protocol Deviation** form and submitted to the Sponsor. If applicable per their reporting requirements, the Investigator or Designee will also report applicable protocol deviations to their IRB.

8. **Study Termination**

Study subject participation is expected to end upon completion of the subject's 2 year follow-up visit unless the subject voluntarily withdraws from the study, is withdrawn from the study by the Investigator, is lost to follow-up, undergoes revision to remove a study device, or expires. Reason(s) for study completion must be documented on the **Study Completion** form.

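### Investigator withdrawal for lost eligibility (X.D.4) is not limited to the time before implantation, so a subject with an infected study knee could leave before a possible revision and be censored

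*Combined protocol and SAP*

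**What the plan says.** Section X.D.4 (Investigator Withdrawal) reads: "The Investigator can choose to withdraw a subject from the study if the subject no longer meets study inclusion/exclusion criteria". The only other requirement there is that the reason be recorded on the Study Completion form. X.D.5, on withdrawal by the subject, also asks for a final evaluation where possible; X.D.4 does not.

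IX.J says that data are collected until the subject completes the study or leaves early, and its list of early exits includes a subject who "is withdrawn from the study by the investigator, is lost to follow-up, undergoes revision to remove a study device, or expires". X.D.8 repeats the list for the end of participation: "is withdrawn from the study by the Investigator, is lost to follow-up, undergoes revision to remove a study device, or expires". In both, investigator withdrawal stands apart from revision.

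Under IX.C a subject is enrolled at consent and becomes active on receiving the device. If a "subject does not receive the study device at the time of surgery", that case is closed as a screen failure.

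Two exclusion criteria in VII.B concern infection: "Previous history of infection in the affected joint" (criterion 1) and "Active local or systemic infection that may affect the prosthetic joint" (criterion 2). Section XI lists infection among the risks of the operation. X.E.4 defines an outcome, Study Withdrawal, for a subject withdrawn because of an adverse event, and a separate one for revision or removal of the device.

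Freedom from revision for any reason at 2 years is a secondary endpoint (VI). XII.A summarizes implant survival by Kaplan-Meier and does not say how withdrawn subjects are handled.

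**The concern.** Criterion 2 mentions the prosthetic joint, and a postoperative infection of the study knee fits the wording of both infection criteria. Such a subject can be said to meet eligibility no longer, and X.D.4 then leaves withdrawal to the investigator's discretion. Infection is also a complication that may lead to revision. Withdrawing the subject for it would remove someone from the risk set for a reason tied to the event being counted, whereas Kaplan-Meier assumes that censoring is unrelated to later risk.

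The direction favors the device. Each arm is a small, uncontrolled single arm, so no comparator would carry the same bias. Section XII allows the descriptive summaries to support regulatory submissions and publications, so the survival figure may be used outside the study.

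**Working it through.** **Step 1. Can the rule reach implanted subjects?**

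- X.D.4 has no time limit, and its wording describes a change after entry.
- IX.J and X.D.8 put investigator withdrawal among the exits from postoperative follow-up.
- X.E.4 foresees withdrawal because of an adverse event.
- Subjects who never receive the device already leave as screen failures (IX.C). The X.D.4 exits that can alter results are therefore those after implantation.

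Taken together, the text permits it.

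**Step 2. Would a later revision be captured?** IX.J ends data collection at withdrawal. X.D.2 asks for changes in the outcome of complications to be updated during the study. X.E.3 requires a device report with x-rays and operative notes for events of uncertain, probable or definite relation to the device. These may catch some later revisions, but no section requires revision status to be checked after withdrawal. Capture is possible and not assured.

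**Step 3. Size, as an illustration.**

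Inputs from XII.B: 66 enrolled per arm and 12% loss, giving 66 × 0.88 = 58.08, taken as 58. The plan's own figures reproduce, though this point does not depend on them. With a null of 0.98 − 0.10 = 0.88, an alternative of 0.98 and 80% power, the one-sample normal formula at two-sided 0.05 gives 56.96, so 57. Allowing for loss, 57/0.88 = 64.8, so 65, against the stated approximate 66.

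Assumptions, not in the documents: k = 1, 2 or 3 true revisions per arm, at 6, 9 and 12 months; all other subjects followed to 24 months; the subject with the first revision is instead withdrawn at 3 months, censored, and the revision never recorded.

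- All revisions counted: S = (n − k)/n.
- One withdrawn before revision: S = (n − k)/(n − 1).
- Difference: (n − k)/[n(n − 1)].

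| n | k | All counted | One censored | Difference (points) |
|---|---|---|---|---|
| 66 | 1 | 65/66 = 98.48% | 65/65 = 100% | 1.52 |
| 66 | 2 | 64/66 = 96.97% | 64/65 = 98.46% | 1.49 |
| 66 | 3 | 63/66 = 95.45% | 63/65 = 96.92% | 1.47 |
| 58 | 1 | 57/58 = 98.28% | 57/57 = 100% | 1.72 |
| 58 | 2 | 56/58 = 96.55% | 56/57 = 98.25% | 1.69 |
| 58 | 3 | 55/58 = 94.83% | 55/57 = 96.49% | 1.66 |

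For n = 66 and k = 2, the log-log 95% interval moves from 88.4–99.2% to 89.6–99.8%. The shift per exit is small against the width of the interval, but it always goes upward.

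**The case against.** The strongest reply is that the rule was never meant as a continuing test. The eligibility form is among the preoperative documents in IX.G ("Preoperative data will be collected on the following source documents") and is absent from the follow-up forms in IX.J ("Postoperative follow-up clinical data will be collected on the following source document forms"). Criterion 1 is phrased as history. Criterion 10 excludes earlier arthroplasty of the same knee; applied after surgery, every implanted subject would fail it. X.D.4 also has an ordinary use between consent and surgery, and the lists in IX.J and X.D.8 are generic. Most of this stands: preoperative status was probably intended. But X.D.4 does not say so, and the Study Withdrawal outcome in X.E.4 shows that withdrawal because of a complication was contemplated.

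It is also true that withdrawal is optional, that its reason is recorded, and that the infection itself must be reported as an adverse event. These make the exit visible; they do not supply the later revision status. The lack of a rule in XII for analyzing any early exit is a wider gap. X.D.4 differs in that the exit is discretionary and may be triggered by the complication itself.

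Two stronger readings are tempting and not supported. A reader might infer that every revision after withdrawal is lost; X.D.2 and X.E.3 leave room for some to be captured. A reader might also infer that one such exit could reverse the primary-endpoint result. No exclusion criterion names radiolucency, and XII.B states neither the test nor its sidedness. Under the z-test whose formula gives 57, 2 failures in 57 already meet the 88% bound: z = (0.9649 − 0.88)/√(0.88 × 0.12/57) = 1.973, one-sided p = 0.0243. In that example nothing is left to reverse.

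**Conclusion.** The point holds as a gap in wording with a plausible bias in one direction. The text allows an implanted subject to be withdrawn because of a study-knee infection, and a later revision is then not assured to be recorded. If the subject is censored, revision-free survival could be too high by about 1.5 to 1.7 percentage points per exit.

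That size rests on assumed counts of 1 to 3 revisions in 58 to 66 subjects, on otherwise complete follow-up, and on the withdrawn subject truly going on to revision unrecorded. How often this would happen is unknown, because the documents give no withdrawal, infection or revision rate. No goal or test is set for revisions, so what could shift is a descriptive estimate. No claim is made about the primary-endpoint test, and nothing here shows that the sponsor intended to remove complications from the data. This is a cheap improvement and does not show that the design is unsound.

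**What to change.** The changes concern data collection and analysis only, not treatment.

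- **X.D.4.** Add: *Eligibility is judged on preoperative status. After implantation, a complication of the study knee that would meet an exclusion criterion is not in itself a reason for investigator withdrawal from data collection. Follow-up for radiographs, Oxford Knee Score, revision status and adverse events continues unless the subject withdraws consent, is lost to follow-up, is revised or dies.*
- **IX.J and X.D.8.** Where investigator withdrawal is listed, add a cross-reference to X.D.4.
- **X.E.4.** Reconcile the Study Withdrawal outcome with the revised X.D.4.
- **XII.A.** List investigator withdrawals after implantation by arm, with date, reason and study-knee status at exit. Add a sensitivity Kaplan-Meier analysis that counts as a revision only those subjects withdrawn with a study-knee infection, or with another complication type defined in advance. A looser category, such as any unresolved complication, could sweep in pain or swelling and should be avoided.

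The cost is a few sentences, slightly more follow-up work at sites, and one extra listing and one extra table per arm.

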Performance of the commercially available *NexGen TM Monoblock Tibia* and *NexGen TM Modular Tibia* used in primary cementless tibia total knee arthroplasty will be evaluated for radiographic parameters, pain and function, and survival of the device. Data collected in this study will be summarized descriptively and descriptive summaries will be the basis of any study reports issued. These summaries may be used for interim study reports and may also be used to support regulatory submissions, presentations, and/or publications. Additional surgical technique and instrumentation data may be collected and evaluated.

A. General Statistical Methods

Statistical methodology will consist of summarizing collected data descriptively. Categorical data (e.g., gender or race) will be summarized using counts and percentages, and 95% Confidence Interval (CI), over the time periods of interest. Continuous data, such as age, will be summarized by using means, medians, standard deviation, minimum, maximum, and 95% CI over the time periods of interest. Implant survival and return to function will be summarized using a Kaplan-Meier method and presented with rates (as percentages) and confidence intervals.

B. Sample Size

A minimum of 132 subjects are to be enrolled in this study, with approximate equal distribution of at least 66 *NexGen TM Monoblock* and 66 *NexGen TM Modular* subjects. The *NexGen TM Monoblock Tibia* and *NexGen TM Modular Tibia* are considered 2 single-arms being analyzed separately. Sample size is based upon 6 to 10 sites enrolling between 22 to 30 subjects per site.

Based on *NexGen*'s expected success rate of 98% at two years on the primary endpoint and using a 10% non-inferiority margin against a 98% performance goal, 57 subjects are required to achieve 80% power to test non-inferiority. 57 subjects also allow the Sponsor to control the Type-1 alpha error at 0.05. Assuming a 12% loss to follow-up over 2 years, approximately 66 subjects need to be enrolled for each single arm.

XIII. References

- [1] ISO 14155:2011(E). Clinical investigation of medical devices for human subjects – Good clinical practice.
- [2] US Food and Drug Administration. eCFR – Electronic Code of Federal Regulations Title 21. Retrieved April 25, 2017, from https://www.ecfr.gov/cgi-bin/text-idx?SID=e0cb187b56d9cb0279bb080f88b8121d&mc=true&tpl=/ecfrbrowse/Title21/21tab_02.pl.

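### A subject missed and not reached at one early visit can be closed as lost to follow-up, with no renewed contact required before the 2-year endpoint

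*Combined protocol and SAP*

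**What the plan says.** Section X.D.6 defines loss to follow-up: "A study subject will be considered lost to follow-up after they have missed a visit and attempts to locate and evaluate the subject" have failed. It does not limit the missed visit to the last one or ask for repeated misses. On the procedure it says "The first three contact attempts should be made by telephone, with additional attempts as outlined in the following table". If three calls go unanswered, "the Investigator or Designee should send a letter to the subject explaining the follow-up agreement per the Informed Consent". If everything fails, or if the subject is reached and chooses to withdraw, "a Study Completion form will be completed and will specify the reason the subject is no longer participating in this study".

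A missed visit has a separate record: "Missed visit(s) also must be documented using the Protocol Deviation form, unless the visit is retrospective". No rule closes a subject who misses a visit, is reached and does not withdraw.

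Section IX.J lists the events that end data collection, among them that the subject "is withdrawn from the study by the investigator, is lost to follow-up, undergoes revision to remove a study device, or expires". Section X.D.8 lists loss to follow-up among the early endings of participation. Section IX.K states the aim, "the expectation is to maintain the highest possible rate of follow-up compliance throughout this study", and its only measure is counselling at consent and at each visit.

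The synopsis and section VI place the primary radiographic endpoint and both secondary endpoints (no revision, OKS above 38) at 2 years. IX.J gives the 2-year window as days 669 to 791. Section XII.B says: "Assuming a 12% loss to follow-up over 2 years, approximately 66 subjects need to be enrolled for each single arm".

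**The concern.** The closing rule is not tied to the visit that supplies the endpoint. A subject who cannot be found at 6 months may be closed about 18 months before the 2-year radiograph is due, although some such people can be found again later. No section asks the site to try at the next interval, to make an attempt in the 2-year window, or to reopen a closed case. The rule can turn a temporary absence into a permanent loss, which sits badly with the aim in IX.K.

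Each such closure gives up a possible 2-year radiograph and OKS, and the chance to learn of a later revision or adverse event. In the Kaplan-Meier summary the knee is censored at closure, so a revision after that date is not counted as an event. The loss may be informative if people who disappear differ in outcome from those who attend; the documents do not show whether they do. Section XII gives no rule for a missing 2-year radiograph, so retention is the main safeguard. Few failures are expected: 2% of 57 is 1.1 per arm, so one unseen failure matters.

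**Working it through.** **Inputs from the documents.** Success rate 98%, margin 10% against a 98% goal (so a null of 88%), power 80%, alpha 0.05 with sidedness not stated, 57 evaluable, 12% loss and 66 enrolled per arm (XII.B). Four postoperative follow-up visits, at 6 weeks, 6 months, 1 year and 2 years (IX.J).

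**Assumptions, not in the documents.** The chance q of being missed and not reached is the same at each visit, and the share r of early losses who return by 2 years is 25% to 50%.

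**1. The plan's own figures.** One-sample normal approximation with the null variance and two-sided alpha 0.05:

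n = [1.96·√(0.88·0.12) + 0.842·√(0.98·0.02)]² / 0.10² = 56.96, so 57. This matches.

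With 12% loss: 57/0.88 = 64.8, so 65. The stated 66 is slightly generous.

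**2. The reserve.** 66 − 57 = 9 subjects, or 13.6%. At the planned 12%, 66 × 0.88 = 58.1 remain.

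**3. The rule as written, each occurrence terminal.** Retained = 66(1−q)⁴.

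- The planned 12% corresponds to q = 1 − 0.88^(1/4) = 3.1%. Losses at the first three visits are then 1 − (1−q)³ = 9.1%, about 6 of 66. That is roughly three quarters of all losses (9.1/12).
- 57 are kept up to q = 1 − (57/66)^(1/4) = 3.6%.
- q = 4%: 66 × 0.8493 = 56.1.
- q = 5%: 66 × 0.8145 = 53.8.

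**4. Subjects kept active.** Retained = 66[(1−q)⁴ + (1−(1−q)³)·r·(1−q)]. The second term counts early losses who return and are also seen at 2 years.

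| q per visit | Rule as written | r = 25% | r = 50% |
|---|---|---|---|
| 4% | 56.1 | 57.9 | 59.7 |
| 5% | 53.8 | 56.0 | 58.2 |

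The gain is about 2 to 4 subjects per arm.

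**5. Power by the formula in step 1.** About 79% at 56.1 and 75% at 53.8, against 80% at 57.

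**The case against.** The strongest reply is that the rule is narrower than it looks and that the plan already budgets for it. Most of this stands.

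- A reader might infer that one missed visit closes the case. It does not: the calls and the letter must also fail. Only the unreachable subset is affected.
- A reader might infer that later contact is barred. It is not. X.D.6 sets no deadline for the attempts or for filing the form, and its wording allows for more than one missed visit. The gap is that renewed contact is not required. The letter refers to the consent form; neither that form nor the Study Completion form is in the text reviewed, so any re-contact terms there could not be checked.
- A reader might infer that 66 per arm is too few. The 12% is for loss over the whole 2 years, so it includes early losses, and it leaves 58.1. A shortfall below 57 appears only above about 3.6% per visit, and no per-visit rate is given. The 66 is also a minimum: with 70 in an arm, 5% per visit leaves 70 × 0.8145 = 57.0.
- The remedy is partial. Someone who stays unreachable is lost under either rule, and at 5% with a quarter returning, 56.0 is still short of 57.

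What the reply does not remove is the rule itself. X.D.6, IX.J and X.D.8 agree that loss to follow-up ends participation, and a site that follows them may stop well before the endpoint visit. An allowance for numbers also does nothing about bias if the loss is informative.

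**Conclusion.** The point holds as a retention weakness and a cheap improvement. The protocol allows a subject who is missed and not reached at any one early visit to be closed before the 2-year endpoint, and it neither requires another attempt nor provides for reopening. It does not hold as an error in the sample size, as a ban on later contact, or as a forecast that an arm will fall below 57.

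The reading of the text is firm. The size is illustrative: it rests on equal terminal loss at four visits, on assumed return shares of 25% to 50%, and on exactly 66 enrolled. Under these assumptions early closures make up most of the losses, and keeping subjects active recovers about 2 to 4 per arm at 4% to 5% loss per visit. The direction and size of any bias cannot be judged from the documents.

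**What to change.** Amend X.D.6 in three respects.

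1. A subject who is missed and not reached before the 2-year visit stays active. The miss is logged as a Protocol Deviation, as the section already requires for missed visits.
2. The contact procedure is repeated at each remaining interval, including the 2-year window (days 669 to 791).
3. Loss to follow-up is assigned, and the Study Completion form filed for that reason, only after day 791 has passed without contact.

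Subjects who withdraw consent are closed as now. IX.J and X.D.8 should be aligned with the new wording.

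The cost is a short protocol amendment, and at the sites a few extra calls and a letter per missed interval. Some cases stay open longer. No additional patients or scheduled visits are needed, and the added site work should not call for more staff.
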